5.2.3 Assessment of safety laboratory parameters

For the assessment of laboratory parameters, blood and urine samples will be collected by the trial site at the time points indicated in the [Flow Chart](#) after the subjects have fasted for at least 10 h. Overnight fasting is not required at the discretion of the investigator or designee for retests and for safety labs "within period".

The parameters that will be determined are listed in [Tables 5.2.3: 1](#) and [5.2.3: 2](#). Reference ranges will be provided in the ISF.

Manual differential white blood cell count or urine sediment examinations will only be performed if there is an abnormality in the automatic blood cell count or in the urinalysis, respectively.

Proprietary confidential information © 2017 Boehringer Ingelheim International GmbH or one or more of its affiliated companies

Table 5.2.3: 1 Routine laboratory tests

Functional lab group	Test name	SCR	Within period	End-of- trial
Haematology	Haematocrit	x	x	x
	Haemoglobin	x	x	x
	Red blood cell count (RBC)	x	x	x
	White blood cell count (WBC)	x	x	x
	Platelet count	x	x	x
Automatic WBC differential (relative and absolute)	Neutrophils	x	-	x
	Eosinophils	x	-	x
	Basophils	x	-	x
	Monocytes	x	-	x
	Lymphocytes	x	-	x
Manual WBC differential (if automatic is abnormal)	Polymorphnuclear neutrophils (segs)	x	-	x
	Band neutrophils (stabs)	x	-	x
	Eosinophils	x	-	x
	Basophils	x	-	x
	Monocytes	x	-	x
	Lymphocytes	x	-	x
Enzymes	Aspartate transaminase (AST/GOT)	x	x	x
	Alanine transaminase (ALT/GPT)	x	x	x
	Alkaline phosphatase (AP)	x	x	x
	Gamma-glutamyl transferase (GGT)	x	x	x
	Lactate dehydrogenase (LDH)	x	x	x
Hormones	Thyroid stimulating hormone (TSH)	x	-	-
Substrates	Plasma glucose	x	-	x
	Serum creatinine	x	-	x
	eGFR (CKD-EPI for creatinine)	x	-	x
	Total bilirubin	x	x	x
	Direct bilirubin	x	x	x
	Total protein	x	-	x
Electrolytes	C-Reactive Protein (CRP)	x	-	x
	Sodium	x	-	x
	Potassium	x	-	x
Urinalysis (Stix)	Calcium	x	-	x
	Urine nitrite	x	-	x
	Urine protein	x	-	x
	Urine glucose	x	-	x
	Urine ketone	x	-	x
	Urobilinogen	x	-	x
	Urine bilirubin	x	-	x
	Urine erythrocytes	x	-	x
	Urine leukocytes	x	-	x
Urine sediment (microscopic examination if erythrocytes, leukocytes nitrite or protein are abnormal in urine)	Urine pH	x	-	x
	Only positive findings will be reported (for instance, the presence of sediment bacteria, casts in sediment, squamous epithelial cells, erythrocytes, leukocytes)	x	-	x

The tests listed in [Table 5.2.3: 2](#) are exclusionary laboratory tests which may be repeated as required. The results will not be entered in the CRF/database and will not be reported in the

Proprietary confidential information © 2017 Boehringer Ingelheim International GmbH or one or more of its affiliated companies

CTR. Except for drug screening, it is planned to perform these tests during screening only. Drug screening will be performed at screening and at the times indicated in the [Flow Chart](#).

Table 5.2.3: 2 Exclusionary laboratory tests

Functional lab group	Test name
Drug screening (urine)	Amphetamine/MDA Barbiturates Benzodiazepine Cannabis Cocaine Methadone Methamphetamines/MDMA/XTC Opiates Phencyclidine Tricyclic antidepressants
Infectious serology (blood)	Hepatitis B surface antigen (qualitative) Hepatitis B core antibody (qualitative) Hepatitis C antibodies (qualitative) HIV-1 and HIV-2 antibody (qualitative)

To encourage compliance with alcoholic restrictions, a breath alcohol test (Alcotest® 7410, Dräger AG, Lübeck, Germany) will be performed at the start of each treatment period, and may be repeated at any time during the study at the discretion of an investigator or designee. The results will not be included in the CTR.

Laboratory data will be transmitted electronically from the laboratory to the trial site.

5.2.4 Electrocardiogram

Twelve-lead ECGs (I, II, III, aVR, aVL, aVF, V1 - V6) will be recorded using a computerised electrocardiograph (CardioSoft EKG System, GE Medical Systems, Freiburg, Germany) at the time points given in the [Flow Chart](#).

All ECGs will be recorded for 10-sec duration after the subjects have rested for at least 5 min in a supine position. ECG assessment will always precede all other study procedures of the same time point (except blood drawing from an intravenous cannula which is already in place) to avoid impact of sampling on the ECG quality.

All ECGs will be stored electronically on the Muse CV Cardiology System (GE Medical Systems, Freiburg, Germany). Electrode placement will be performed according to the method of Wilson, Goldberger and Einthoven modified by Mason and Likar (hips and shoulders instead of ankles and wrists).

All locally printed ECGs will be evaluated by the investigator or a designee. ECGs may be repeated for quality reasons (like alternating current artefacts, muscle movements, electrode

Proprietary confidential information © 2017 Boehringer Ingelheim International GmbH or one or more of its affiliated companies

dislocation) and the repeated ECG will be used for analysis. Additional (unscheduled) ECGs may be collected by the investigator for safety reasons.

Abnormal findings will be reported as AEs (during the trial) or baseline conditions (at screening) if judged clinically relevant by the investigator. Any ECG abnormalities will be monitored carefully and, if necessary, the subject will be removed from the trial and will receive the appropriate medical treatment.

5.2.5 Assessment of other safety parameters

5.2.5.1 Vital signs

Systolic and diastolic blood pressures (BP) as well as pulse rate (PR) or heart rate (heart rate is considered to be equal to pulse rate) will be measured by a blood pressure monitor (Dinamap Pro 100, GE Medical Systems, Freiburg, Germany) at the times indicated in the [Flow Chart](#), after subjects have rested for at least 5 min in a supine position. All recordings should be made using the same type of blood pressure recording instrument on the same arm if possible.

5.2.5.2 Medical examinations

At screening, the medical examination will include demographics including height and body weight, smoking and alcohol history, relevant medical history and concomitant therapy, review of inclusion and exclusion criteria, review of vital signs (BP, PR), 12-lead ECG, laboratory tests, and a physical examination. At the end of trial examination, it will include review of vital signs, 12-lead ECG, laboratory tests, and a physical examination.

[REDACTED]

5.4 APPROPRIATENESS OF MEASUREMENTS

All measurements performed during this trial are standard measurements and will be performed in order to monitor subjects' safety and to determine pharmacokinetic parameters

Proprietary confidential information © 2017 Boehringer Ingelheim International GmbH or one or more of its affiliated companies

in an appropriate way. The scheduled measurements will allow monitoring of changes in vital signs, standard laboratory values, and ECG parameters that might occur as a result of administration of trial medication. The safety assessments are standard, are accepted for evaluation of safety and tolerability of an orally administered drug, and are widely used in clinical trials. The pharmacokinetic parameters and measurements outlined in Section 5.5 are generally used assessments of drug exposure.

5.5 DRUG CONCENTRATION MEASUREMENTS AND PHARMACOKINETICS

Date and clock time of drug administration and pharmacokinetic sampling will be recorded.

Exact time points of plasma sampling will be derived from the study management system ClinBase™ and documented in the CRFs by the medical personnel or sent as electronic files to the trial data manager. The actual sampling times will be used for determination of pharmacokinetic parameters.

5.5.1 Pharmacokinetic endpoints

5.5.1.1 Primary endpoints

The following primary endpoints will be used to assess the relative bioavailability of BI 425809 in plasma with and without co-administration of rifampicin:

- AUC_{0-168} (area under the concentration-time curve of BI 425809 in plasma over the time interval from 0 to 168 h)
- C_{max} (maximum measured concentration of BI 425809 in plasma)

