Clinical Trial Protocol

Document Number: c13723133-03

EudraCT No.: 2016-004862-24

BI Trial No.: 1346-0018

BI Investigational Product: BI 425809

Title: Effects of rifampicin on the pharmacokinetics of BI 425809 following oral administration in healthy male subjects (an open-label, two-period, fixed-sequence trial)

Clinical Phase: I

Trial Clinical Monitor:

Phone: [REDACTED]

Fax: [REDACTED]

Principal Investigator:

Phone: [REDACTED]

Fax: [REDACTED]

Status: Final Protocol (Revised Protocol (based on global amendment 2))

Version and Date: Version: 3.0 Date: 05 Apr 2017

Page 1 of 61

Proprietary confidential information

© 2017 Boehringer Ingelheim International GmbH or one or more of its affiliated companies. All rights reserved.
This document may not - in full or in part - be passed on, reproduced, published or otherwise used without prior written permission

Proprietary confidential information © 2017 Boehringer Ingelheim International GmbH or one or more of its affiliated companies

CLINICAL TRIAL PROTOCOL SYNOPSIS

Name of company: Boehringer Ingelheim		Tabulated Trial Protocol			
Name of finished product: Not applicable					
Name of active ingredient: BI 425809					
Protocol date: 20 December 2016	Trial number: 1346-0018		Revision date: 05 April 2017		
Title of trial: Effects of rifampicin on the pharmacokinetics of BI 425809 following oral administration in healthy male subjects (an open-label, two-period, fixed-sequence trial)					
Principal Investigator: [REDACTED]					
Trial site: [REDACTED]					
Clinical phase:	I				
Objective:	To investigate whether and to what extent co-administration of multiple doses of rifampicin affect single dose pharmacokinetics of BI 425809 in healthy male subjects and to characterize the single dose pharmacokinetics of the metabolite BI 761036				
Methodology:	Open-label, fixed-sequence trial with 2 treatments (A and B)				
No. of subjects:					
total entered:	16				
each treatment:	16				
Diagnosis:	Not applicable				
Main criteria for inclusion:	Healthy male subjects, age of 18 to 55 years, body mass index (BMI) of 18.5 to 29.9 kg/m ²				
Trial product 1:	BI 425809, 25 mg tablet				
dose:	25 mg as single dose in treatments A and B				
mode of admin.:	Oral administration with 240 mL of water after overnight fast				
Trial product 2:	Eremfat® 600 mg tablet (1 tablet containing 600 mg rifampicin)				
dose:	600 mg once daily (qd) for 10 days in treatment A				

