3.2 DISCUSSION OF TRIAL DESIGN, INCLUDING THE CHOICE OF CONTROL GROUPS

The study will be performed as a randomized, open-label, two period, fixed-sequence trial in healthy male subjects. This study design is considered to be appropriate to investigate the effect of multiple doses of rifampicin on single-dose PK of BI 425809 and to characterise the PK of its major metabolites.

Full induction effect of rifampicin can be expected after 1 week. The baseline activity after discontinuing rifampicin treatment can be attained within 2 weeks [[P03-08008](#)].

Due to the expected long half-life of metabolite BI 761036 a fixed sequence design was selected, with administration of rifampicin in the second study period only. The fixed-sequence design is not expected to lead to systematic errors in the estimation of the treatment effects, because the trial duration is short enough so that nonspecific time-effects are not expected.

The open-label treatment is not expected to bias results, since the study endpoints are derived from measurement of plasma concentrations of the analyte provided by a bioanalytical laboratory.

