4.1.3 Selection of doses in the trial

Rifampicin given at a dosage of 600 mg once daily reflects standard clinical doses and is considered sufficient to yield significant CYP3A4 induction. To avoid any potential interference with rifampicin effects on transporters, BI 425809 and rifampicin are not administered simultaneously.

Proprietary confidential information © 2017 Boehringer Ingelheim International GmbH or one or more of its affiliated companies

The selected dose of BI 425809 (25 mg) corresponds to the estimated therapeutic dose and is expected to provide adequate exposure for the purposes of this trial whilst being safe at the same time.

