5.5.1.2 Secondary endpoint

Additionally, the following secondary endpoint will be evaluated for BI 425809 in plasma:

- $AUC_{0-\infty}$ (area under the concentration-time curve of BI 425809 in plasma over the time interval from 0 extrapolated to infinity)

And further, the following secondary endpoint will be evaluated for BI 761036 in plasma:

- $t_{1/2}$ (terminal half-life of BI 761036 in plasma)

[REDACTED]

[figure not shown]
[REDACTED]

[REDACTED]

[REDACTED]

[REDACTED]

[REDACTED]

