6.2.2 Treatment periods

Each subject is expected to participate in two treatment periods (Days 1 to 43 in period 1, day -6 to 8 in period 2). The administration of BI 425809 in period 1 and 2 will be separated by at least 49 days.

On Day 1 of each treatment period study participants will be admitted to the trial site and kept under close medical surveillance for at least 24 h following drug administration. The

Proprietary confidential information © 2017 Boehringer Ingelheim International GmbH or one or more of its affiliated companies

subjects will then be allowed to leave the trial site after formal assessment and confirmation of their fitness. On all other study days, the study will be performed in an ambulatory fashion.

For details on time points and procedures for collection of plasma samples for PK analysis, refer to [Flow Chart](#) and [Section 5.5.2](#).

The safety measurements performed during the treatment period are specified in [Section 5.2](#) of this protocol and in the Flow Chart. For details on time points for all other trial procedures, refer to the Flow Chart. AEs and concomitant therapy will be assessed continuously from screening until the end of trial examination.

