7.5.2 Secondary endpoints

Analysis of relative BA of secondary endpoint $AUC_{0-\infty}$ of BI 425809 in plasma will be performed in the same way as for the primary endpoints.

No inferential statistical analysis is planned for secondary endpoint $t_{1/2}$ of metabolite BI 761036.

Secondary PK endpoints will be assessed descriptively. The analysis of standard PK parameters is performed according to BI standards ([5](#)) [001-MCS-36-472_RD-01].

See [Section 7.4](#) of this TSAP for details regarding exclusion of PK parameters and plasma concentrations.

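### Does cutting the primary AUC at 168 h hide part of the rifampicin effect, so that AUC0-inf should be primary instead?

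*Protocol*

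**What the plan says.** Protocol 5.5.1.1 names two primary endpoints for BI 425809 in plasma: Cmax and AUC0-168, the latter defined as the "area under the concentration-time curve of BI 425809 in plasma over the time interval from 0 to 168 h". Protocol 5.5.1.2 then adds AUC0-inf as secondary, the "area under the concentration-time curve of BI 425809 in plasma over the time interval from 0 extrapolated to infinity". The synopsis states the aim as "To investigate whether and to what extent co-administration of multiple doses of rifampicin affect single dose pharmacokinetics of BI 425809".

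The two AUCs are treated alike. Protocol 7.3.1 lists AUC0-168, Cmax and AUC0-inf together for log transformation, ANOVA and 90% confidence interval. SAP 7.5.2 confirms that the analysis of AUC0-inf "of BI 425809 in plasma will be performed in the same way as for the primary endpoints". Protocol 7.2 sets no acceptance range and plans no hypothesis test.

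The two periods differ in length: "Days 1 to 43 in period 1, day -6 to 8 in period 2" (Protocol 6.2.2). In the Flow Chart the last test-period plasma sample is at 168 h, the one before it is at 96 h, and the last rifampicin dose is at 82 h. Reference-period sampling continues past 168 h, to at least 504 h as far as the column layout can be read.

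**The concern.** The plan expects rifampicin to act by induction. The dose is "considered sufficient to yield significant CYP3A4 induction" (Protocol 4.1.3), and BI 425809 is given on the seventh rifampicin day because "Full induction effect of rifampicin can be expected after 1 week" (Protocol 3.2). Faster elimination shortens the test-period tail, so a common cut at 168 h removes mainly reference AUC.

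The direction of the resulting shift is known before any data exist: the ratio moves towards no interaction. To a first approximation, the point estimate and both confidence limits move by the same factor. The trial collects the reference tail and then leaves it out of its headline exposure measure. Since the aim is to say how large the interaction is, a headline that understates it looks like the wrong choice when AUC0-inf is calculated anyway.

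**Working it through.** The visible documents give no half-life, expected ratio or extrapolated share, so there is no stated figure to reproduce. The check is a sensitivity calculation.

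**Inputs**
- Window: 168 h in both periods (Protocol 5.5.1.1).
- Parent half-life: assumed, 30 to 100 h. The only indirect pointer is the residual effect period of 11 days (Protocol 5.2.2.2). If that were five half-lives, which the protocol does not say, the half-life would be 264/5 = 52.8 h.
- Absorption rate constant ka: 0.8/h, assumed.
- Induction: elimination rate multiplied by f, from 1.5 to 10, assumed.

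**Formulas** (one compartment, oral dose)
- Reference rate k = ln 2 / half-life; test rate = f·k.
- Share of AUC after 168 h: L(k) = [ka·exp(-168k) - k·exp(-168ka)] / (ka - k).
- True AUC ratio = 1/f.
- Shift factor = AUC0-168 ratio / AUC0-inf ratio = [1 - L(f·k)] / [1 - L(k)].

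**Worked case: half-life 52.8 h, f = 3**
- Reference: k = 0.01313, exp(-2.205) = 0.1102, times 0.8/0.7869 gives L = 0.112.
- Test: 3k = 0.0394, which gives L = 0.0014.
- Shift factor = 0.9986/0.888 = 1.125. A true ratio of 0.333 appears as 0.375.

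**Range**

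| Half-life (h) | Reference AUC lost | Test AUC lost, f = 1.5 | Upward shift of ratio, f = 2 to 10 |
|---|---|---|---|
| 30 | 2.1% | 0.3% | about 2% |
| 40 | 5.6% | 1.3% | about 6% |
| 52.8 | 11.2% | 3.8% | 11-13% |
| 66 | 17.4% | 7.2% | 17-21% |
| 80 | 23.6% | 11.5% | 24-31% |
| 100 | 31.5% | 17.7% | 31-46% |

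Three qualifications follow.
- The loss is nearly confined to the reference only when induction is roughly 2- to 3-fold or stronger, or the half-life is short. At f = 1.5 and 52.8 h the shift is about 8%.
- If rifampicin acted only on first-pass bioavailability, both tails would shrink in proportion and the shift would be zero.
- At 52.8 h and f = 5, the AUC0-168 ratio is about 0.23 against 0.20, a reported reduction of 77% instead of 80%.

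**How well AUC0-inf does in the test period.** I let induction wane after rifampicin stops (held to 94 h, enzyme turnover half-life 36 h, both assumed) and took the terminal slope from the 72, 96 and 168 h samples, with f = 2.

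| Half-life (h) | True ratio | AUC0-inf ratio as estimated | AUC0-168 ratio |
|---|---|---|---|
| 52.8 | 0.516 | 0.510 | 0.561 |
| 80 | 0.548 | 0.525 | 0.626 |
| 100 | 0.575 | 0.535 | 0.667 |

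AUC0-inf is about 1%, 4% and 7% low. It is closer to the truth than AUC0-168 throughout, but its own error grows where the truncation is worst.

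**What the label controls.** Both ratios come from the same model, the same analysis set and the same interval. No significance level, testing order or acceptance range is attached to the primary endpoints. Exchanging the labels leaves every estimate and interval as it is.

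**The case for a change.** The strongest case for a change is that this trial delivers only estimates, so bias matters as much as precision. With 16 paired subjects and an assumed intra-subject CV of 15% or 20%, the 90% limits lie a factor of exp(1.753·σ·√(2/16)) from the estimate, with σ² = ln(1 + CV²). That is about 10% or 13% on the upper side. At a half-life near 53 h the truncation shift is of the same order, so the AUC0-168 interval taken alone could cover the full exposure ratio poorly. The simulation also favours AUC0-inf at every half-life tried, and both parameters are already computed.

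The direction and the advantage of AUC0-inf as a measure of total exposure both stand. They are reasons to read the AUC0-inf result, which the plan already delivers with full inference.

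Two further points weigh against an exchange. First, 0-168 h is the longest span observed in both periods and needs almost no extrapolation. Test-period AUC0-inf depends on a terminal slope with no sample between 96 and 168 h, fitted while induction may be fading, and it may be missing where that slope cannot be estimated. Second, replacing a primary endpoint is a protocol amendment needing ethics committee and authority approval (Protocol 8.1). The basis for 16 subjects is not visible, so it is unknown whether it was built on AUC0-168.

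Asking instead for a stated reason for 168 h gains little, because that reason may lie in the blacked-out text.

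**Conclusion.** No change to the plan. If induction shortens elimination, the AUC0-168 ratio understates the interaction. The relative shift is about 2% at a half-life of 30 h, 6% at 40 h, 11-13% at 53 h and more beyond that, for 2- to 10-fold induction. It is smaller for weak induction and zero for a purely first-pass effect. These figures rest on a one-compartment model and on a half-life that the visible documents do not give; the 53 h value is a reading of the residual effect period, not a stated fact.

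The exchange brings no gain, since the untruncated ratio is prespecified with identical analysis and nothing is decided on the primary label. Keeping the common observed window as primary, with AUC0-inf beside it, is a fair trade-off. Analysts will have both ratios and can conclude on the extent of the interaction from the two together.

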5.5.1.2 Secondary endpoint

Additionally, the following secondary endpoint will be evaluated for BI 425809 in plasma:

- $AUC_{0-\infty}$ (area under the concentration-time curve of BI 425809 in plasma over the time interval from 0 extrapolated to infinity)

And further, the following secondary endpoint will be evaluated for BI 761036 in plasma:

- $t_{1/2}$ (terminal half-life of BI 761036 in plasma)

[REDACTED]

[figure not shown]
[REDACTED]

[REDACTED]

[REDACTED]

[REDACTED]

[REDACTED]

5.5.2 Methods of sample collection

5.5.2.1 Plasma sampling for pharmacokinetic analysis

For quantification of BI 425809 plasma concentrations, 2.7 mL of blood will be taken from an antecubital or forearm vein into a K₃-EDTA (tripotassium ethylenediaminetetraacetic acid)-anticoagulant blood drawing tube at the times indicated in the [Flow Chart](#).

For quantification of metabolites BI 761036, [REDACTED] plasma concentrations, 2.7 mL of blood will be taken from an antecubital or forearm vein into a K₃-EDTA-anticoagulant blood drawing tube at the times indicated in the Flow Chart.

Blood will be withdrawn by means of either an indwelling venous catheter or by venipuncture with a metal needle.

Blood samples will be centrifuged for about 10 min at about 2000 g to 4000 g and 4 to 8 °C. Two plasma aliquots will be obtained from each blood sample and stored in polypropylene tubes. The first aliquot should contain at least 0.5 mL plasma. The process from blood collection until transfer of plasma aliquots into the freezer should be completed within 60 min with interim storage of blood samples on ice. For each aliquot the time when the sample was placed in the freezer will be documented. Until transfer on dry ice to the analytical laboratory, the aliquots will be stored upright at about -20°C or below at the trial site. The second aliquot will be transferred to the analytical laboratory after the bioanalyst has acknowledged safe arrival of the first aliquot. At the analytical laboratory the plasma samples will be stored at about -20°C or below until analysis.

Proprietary confidential information © 2017 Boehringer Ingelheim International GmbH or one or more of its affiliated companies

At a minimum, the sample tube labels should list the following information: BI trial number, subject number, visit, planned sampling time, and analyte. Further information such as matrix may also be provided.

After completion of the trial the plasma samples may be used for further methodological investigations, e.g. for stability testing, assessment of metabolites. However, only data related to the analyte and/or its metabolite(s) including anti-drug antibodies (if applicable) will be generated by these additional investigations. The study samples will be discarded after completion of the additional investigations but not later than 5 years upon the final study report has been signed.

